## APPENDIX VI - 2016 WHO Classification for CMML and MDS WHO CMML

WHO Subtype	Peripheral Blood	Bone Marrow
	*<2% blasts	*<5% blasts
	**≥2% and <5% blasts	**≥5% and
	***≥5% and <20% blasts	<10% blasts
	persistent monocytosis >1 × 10  /L and >10% of differential	***<20% blasts
#Chronic Myelomonocytic Leukemia	± cytopenias	>10% dysplasia
*CMMML-0	Leukocytosis frequent	in affected lineage
**CMMML-1		***Auer Rods
***CMMML-2		The absence of the Philadelphia chromosome of bcr-abl fusion gene.

#Not meeting WHO criteria for *BCR-ABL1* CML, PMF, PV, or ET. No evidence of *PDGFRA*, *PDGFRB*, or *FGFR1* rearrangement or *PCM1-JAK2* (should be specifically excluded in cases with eosinophilia). If myelodysplasia is absent or minimal, CMML diagnosis can be made with acquired clonal cytogenetic/molecular genetic abnormality or monocytosis × 3 months when all other causes of monocytosis have been excluded. Blasts and blast equivalents include myeloblasts, monoblasts, and promonocytes

## WHO MDS

WHO Category	Peripheral blood	Bone marrow
MDS with single lineage dysplasia (MDS-SLD)	Cytopenia (1-2 lines) <1% blasts	Dysplasia (1 line) <5% blasts RS <15%/ † >5% †
MDS with ring sideroblasts (MDS-RS)*	Cytopenia (1-3 lines) <1% blasts	Dysplasia (1-3 lines) <5% blasts RS >15%/ † >5% †
MDS with multi-lineage dysplasia (MDS-MLD)	Cytopenia (1-3 lines) <1% blasts	Dysplasia (2-3 lines) <5% blasts RS <15%/ † >5% †
MDS with excess blasts type I & II (MDS-EB-1 & MDS-EB-2**)	Cytopenia (0-3 lines) Type I: 2-4% blasts Type II: 5-19% blasts	Dysplasia (1-3 lines) Type I 5-9% blasts Type II 10-19% blasts
MDS with isolated del(5q)***	Cytopenia (1-2 lines) <1% blasts	Dysplasia (1-3 lines) < 5% blasts
MDS unclassified (MDS-U)****	Cytopenia (0-3 lines) 1% or <1% blasts	Dysplasia (1-3 lines) <5% blasts

Cytopenias defined as: hemoglobin <10 g/dL; platelet count <100 × 10^9/L; and absolute neutrophil count <1.8 × 10^9/L.

To be classified as dysplasia, >10% of any cell lineage must be dysplastic. PB monocytes must be <1 × 10^9/L.

†If *SF3B1* mutation is present.

\* Subclassified as MDS-RS with single or multi-lineage dysplasia (MDS-RS-SLD or MDS-RS-MLD). Pancytopenia with RS is classified as MDS-RS-MLD.

\*\* Presence of Auer rods is classified as MDS-EB-2.

\*\*\* Del(5q) alone or with 1 additional abnormality except -7 or del(7q).

\*\*\*\* 1% peripheral blasts need to be confirmed on 2 separate occasions to make a diagnosis of MDS-U. MDS-U diagnosis is also made with SLD and pancytopenia or MDS defining cytogenetic abnormality in the absence of cytopenias.

## APPENDIX VII – *TP53* Sequence Variant Interpretation Algorithm

Inclusion of subjects in the study is based on *TP53* sequencing performed in a laboratory at each participating site according to established local routines. A study-specific variant interpretation algorithm will be used to discriminate between eligible and non-eligible *TP53* sequence variants.

In order to select subjects with high unmet medical need due to poor prognosis, the study will enroll subjects that have any *TP53* mutation which is not pre-defined as 'benign' or 'likely benign'. The operational definition of 'eligible *TP53* mutation' in this clinical study therefore includes variants classified as pathogenic, likely pathogenic and variant of uncertain significance (VUS) in a specified database (UMD-*TP53*). Subjects harboring at least one such *TP53* sequence variant are eligible for inclusion, while subjects who only have variant(s) classified as benign or likely benign are not eligible. Thus, also *TP53* VUS are eligible, avoiding exclusion of subjects with possible pathogenic *TP53* variants presently classified as VUS.

[figure not shown]
The basic parameters for *TP53* sequencing are listed in [Table 17](#).

**Table 17. Basic parameters for *TP53* sequencing and interpretation.**

Sequencing method 	

Any NGS method (amplicon, hybrid capture) that has been validated locally for sequencing TP53

Covers TP53 exons 2-11

Data processing 	Use HGVS nomenclature: http://varnomen.hgvs.org  Reference sequences 

genomic: hg19 or HG38 (do not use hg18)

cDNA: NM_000546.5

Protein: NP_000537.3

Data interpretation   5-tier classification of functional impact on p53: Pathogenic, likely pathogenic, VUS, likely benign, benign	Pathogenic, likely pathogenic or variant of uncertain significance (VUS):  

Frameshift mutations

Nonsense mutations

Donor / acceptor splice sites +/- 2

Synonymous mutations with splice impact

Missense with functional impact

 
→ Eligible for inclusion in the clinical study
 Benign or likely benign:

	

• Synonymous mutations without functional impact

• Missense without functional impact*

 
→ Not eligible for inclusion in the clinical study
 
*A list derived from the UMD-TP53 database is provided as common reference for variant interpretation, see Table 18 and Table 19.

--	--

The *TP53* sequence variant interpretation algorithm is shown below.

**Figure 4. Algorithm for *TP53* variant interpretation.**

Abbreviations for pathogenicity criteria: Fr, Ns, Sp, Ps, Ms (Bg = benign). VUS = Variant of unknown significance.

Thus, the following criteria (for variant classification or variant type) define each variant according to the type of event:

Fr - Frameshift, whether they are in or out of frame

Ns - Nonsense

Sp - Splice

Ps - Pathogenic synonymous (according to the list in [Table 18](#))

Ms - Missense (not in the list of benign variants in [Table 19](#))

Bg - Benign (relevant to report if multiple variants present in the same subject)

The pre-defined lists are presented below, for pathogenic synonymous, Ps ([Table 18](#)) and benign missense, Bg ([Table 19](#)).

**Table 18. Listing of synonymous variants with pathogenic splice impact**

cDNA_Variant_NM_000546.5	NG_017013.2_Variant	HG19_Variant	HG38_Variant	TP53_alpha_NP_000537.3
c.375G>A	NG_017013.2:g.16557 G>A	chr17:g.757931 2G>A	chr17:g.7675994G>A	p.T125=
c.375G>T	NG_017013.2:g.16557 G>T	chr17:g.757931 2G>T	chr17:g.7675994G>T	p.T125=
c.375G>C	NG_017013.2:g.16557 G>C	chr17:g.757931 2G>C	chr17:g.7675994G>C	p.T125=
c.672G>A	NG_017013.2:g.17692 G>A	chr17:g.757817 7G>A	chr17:g.7674859G>A	p.E224=
c.993G>A	NG_017013.2:g.19016 G>A	chr17:g.757685 3G>A	chr17:g.7673535G>A	p.Q331=

**Table 19. Listing of benign or likely benign *TP53* variants to be used for exclusion**

cDNA_Variant_NM_000546.5	NG_017013.2_Variant	HG19_Variant	HG38_Variant	TP53_alpha_NP_000537.3
c.31G>C	NG_017013.2:g.15987G>C	chr17:g.7579882G>C	chr17:g.7676564G>C	p.E11Q
c.91G>A	NG_017013.2:g.16164G>A	chr17:g.7579705G>A	chr17:g.7676387G>A	p.V31I
c.139C>T	NG_017013.2:g.16321C>T	chr17:g.7579548C>T	chr17:g.7676230C>T	p.P47S
c.145G>C	NG_017013.2:g.16327G>C	chr17:g.7579542G>C	chr17:g.7676224G>C	p.D49H
c.173C>G	NG_017013.2:g.16355C>G	chr17:g.7579514C>G	chr17:g.7676196C>G	p.P58R
c.215C>G	NG_017013.2:g.16397C>G	chr17:g.7579472C>G	chr17:g.7676154C>G	p.P72R
c.217G>A	NG_017013.2:g.16399G>A	chr17:g.7579470G>A	chr17:g.7676152G>A	p.V73M
c.248C>T	NG_017013.2:g.16430C>T	chr17:g.7579439C>T	chr17:g.7676121C>T	p.A83V
c.319T>C	NG_017013.2:g.16501T>C	chr17:g.7579368T>C	chr17:g.7676050T>C	p.Y107H
c.329G>A	NG_017013.2:g.16511G>A	chr17:g.7579358G>A	chr17:g.7676040G>A	p.R110H
c.460G>A	NG_017013.2:g.17399G>A	chr17:g.7578470G>A	chr17:g.7675152G>A	p.G154S
c.566C>T	NG_017013.2:g.17586C>T	chr17:g.7578283C>T	chr17:g.7674965C>T	p.A189V
c.665C>T	NG_017013.2:g.17685C>T	chr17:g.7578184C>T	chr17:g.7674866C>T	p.P222L
c.704A>G	NG_017013.2:g.18292A>G	chr17:g.7577577A>G	chr17:g.7674259A>G	p.N235S
c.847C>T	NG_017013.2:g.18778C>T	chr17:g.7577091C>T	chr17:g.7673773C>T	p.R283C
c.869G>A	NG_017013.2:g.18800G>A	chr17:g.7577069G>A	chr17:g.7673751G>A	p.R290H
c.883C>T	NG_017013.2:g.18814C>T	chr17:g.7577055C>T	chr17:g.7673737C>T	p.P295S
c.935C>G	NG_017013.2:g.18958C>G	chr17:g.7576911C>G	chr17:g.7673593C>G	p.T312S
c.1015G>A	NG_017013.2:g.21857G>A	chr17:g.7574012G>A	chr17:g.7670694G>A	p.E339K

c.1073A>T	NG_017013.2:g.21915A>T	chr17:g.7573954A>T	chr17:g.7670636A>T	p.E358V
c.1079G>C	NG_017013.2:g.21921G>C	chr17:g.7573948G>C	chr17:g.7670630G>C	p.G360A
c.1096T>G	NG_017013.2:g.21938T>G	chr17:g.7573931T>G	chr17:g.7670613T>G	p.S366A

Examples of results:

HG19_Variant	cDNA_Variant _NM_000546.5	TP53_alpha_NP_000537 .3	Criterion
chr17:g.7578406G>A	c.524G>A	p.R175H	Ms

Missense variant hot spot

HG19_Variant	cDNA_Variant _NM_000546.5	TP53_alpha_NP_000537 .3	Criterion
chr17:g.7578212C>T	c.637C>T	p.R213*	Ns

Nonsense variant hot spot

HG19_Variant	cDNA_Variant _NM_000546.5	TP53_alpha_NP_000537 .3	Criterion
chr17:g.7578223_7578222 del	c.626_627del	p.(R209Kfs*6)	Fr

Indel variant hot spot (deletion)

HG19_Variant	cDNA_Variant _NM_000546.5	TP53_alpha_NP_000537 .3	Criterion
chr17:g.7579471dup	c.216dup	p.(V73Rfs*76)	Fr

Indel variant hot spot (duplication)

HG19_Variant	cDNA_Variant _NM_000546.5	TP53_alpha_NP_000537 .3	Criterion
chr17:g.7574005_7574004ins A	c.1022_1023ins A	p.(F341Lfs*6)	Fr

Indel variant hot spot (Insertion)

HG19_Variant	cDNA_Variant _NM_000546.5	TP53_alpha_NP_000537 .3	Criterion
chr17:g.7578555G>A	c.376-1G>A	p.?	Sp

Splice site variant

HG19_Variant	cDNA_Variant _NM_000546.5	TP53_alpha_NP_000537 .3	Criterion
chr17:g.7579312G>A	c.375G>A	p.T125=	Ps

Pathogenic synonymous variant

HG19_Variant	cDNA_Variant _NM_000546.5	TP53_alpha_NP_000537 .3	Criterion
1202_CSP_6.0	105 of 106		10 September 2021

chr17:g.7579472C>G	c.215C>G	p.P72R	Bg
chr17:g.7578210A>G	c.639A>G	p.R213=	Bg

Non-pathogenic common SNPs

HG19_Variant	cDNA_Variant _NM_000546.5	TP53_alpha_NP_000537 .3	Criterion
chr17:g.7578561C>T	c.376-7C>T	p.(=)	Bg

Intronic mutation

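### The chr17 entries in the TP53 eligibility lists (Appendix VII, Tables 18 and 19) carry transcript-strand alleles on coordinates that run the other way, so a laboratory matching the exact chr17 string could misclassify a subject whose only variant is listed

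*Combined protocol and SAP*

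**What the plan says.** Inclusion criterion 2 (Section 4.7) refers to Appendix VII for the definition of an eligible TP53 mutation. Sequencing is done locally at each site, and the Synopsis allows up to 10 centers.

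Table 17 instructs laboratories: "Use HGVS nomenclature". It allows a genomic reference ("genomic: hg19 or HG38 (do not use hg18"), a transcript reference ("cDNA: NM_000546.5") and a protein reference. It adds that a list derived from the UMD-TP53 database "is provided as common reference for variant interpretation", meaning Tables 18 and 19.

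The criteria under Figure 4 give the lists their force. The eligible category Ms is defined as "Missense (not in the list of benign variants in" Table 19. A synonymous variant is Ps, also eligible, according to the list in Table 18. Subjects who have only benign or likely benign variants are not eligible.

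Table 18 has 5 rows and Table 19 has 22. Typical chr17 entries are "chr17:g.7579472C>G" beside c.215C>G and, in HG38, "chr17:g.7675994G>A" beside c.375G>A. The worked deletion example begins "chr17:g.7578223_7578222". No readable text says which column a laboratory must match on.

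**The concern.** When two references run in opposite directions along the same DNA, the base read on one is the complement of the base read on the other. A chr17 column and a transcript column for such a gene cannot both show C>G at the same site. If they do, one of them is mislabelled.

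This matters because a failed look-up has a default consequence. A benign missense variant not found in Table 19 falls into Ms and counts as eligible. A splice-affecting synonymous variant not found in Table 18 is not scored Ps. The two errors point in opposite directions, and two sites using different columns could classify the same patient differently. In a first-in-human study whose population is defined by TP53 status, the lists should give one answer whichever column is used.

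**Working it through.** The inputs are all 27 rows of Tables 18 and 19 (25 distinct positions) and the worked examples that follow Table 19. The orientation comes from the printed coordinates, not from outside knowledge of the gene. The one convention used is that a chr17 g. description states forward-strand bases, as the HGVS nomenclature named in Table 17 implies.

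1. **Positions.** If NG_017013.2 and chr17 are antiparallel, NG + HG19 is constant. If the two genome builds run together, HG38 − HG19 is constant.

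| Variant | NG | HG19 | HG38 | NG + HG19 | HG38 − HG19 |
|---|---|---|---|---|---|
| c.31G>C (p.E11Q) | 15987 | 7579882 | 7676564 | 7,595,869 | 96,682 |
| c.215C>G (p.P72R) | 16397 | 7579472 | 7676154 | 7,595,869 | 96,682 |
| c.375G>A (p.T125=) | 16557 | 7579312 | 7675994 | 7,595,869 | 96,682 |
| c.1096T>G (p.S366A) | 21938 | 7573931 | 7670613 | 7,595,869 | 96,682 |

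Both constants hold in 27 of 27 rows. As the cDNA position rises from 31 to 1096, NG rises and chr17 falls. The positions reproduce, and chr17 runs opposite to the transcript.

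2. **Alleles.** The cDNA, NG, HG19 and HG38 columns print identical alleles in 27 of 27 rows. Given step 1, the NG and chr17 columns cannot both be right.

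3. **Which columns are wrong.** The printed alleles can be tested against the stated amino-acid change with the genetic code. For c.215C>G, position 215 is the second base of codon 72. Proline is CCN, and C>G there gives CGN, arginine, as stated. The complement, G>C, cannot start from a proline codon. Across Table 19 the printed alleles give the stated change in 22 of 22 rows and their complements in 0 of 22. In Table 18 the printed alleles fit in 5 of 5 rows and the complements in 3 of 5, because any third base encodes threonine at codon 125; that table alone is less decisive. The printed alleles are therefore transcript-strand, and the error lies in the two chr17 columns: 27 × 2 = 54 entries.

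4. **Look-up by exact chr17 string.** The forward-strand call keeps the position and complements both bases:
   - p.P72R: chr17:g.7579472G>C (HG38 chr17:g.7676154G>C)
   - p.E11Q: chr17:g.7579882C>G
   - p.N235S: chr17:g.7577577T>C
   - c.375G>A: chr17:g.7579312C>T

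   Complementing always changes the reference base, so no substitution equals its own complement. Exact matches are 0 of 22 in Table 19 and 0 of 5 in Table 18, for HG19 and HG38 alike. Matching on cDNA or protein notation finds 22 of 22 in Table 19, and so does chr17 position alone.

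5. **Worked examples.** All seven substitution examples repeat the pattern in their HG19 column, for instance chr17:g.7578406G>A beside c.524G>A. The deletion (7578223_7578222) and the insertion (7574005_7574004insA) list chr17 positions from high to low, which is transcript order. The pattern is systematic, so a text-extraction fault does not explain it.

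**The case against.** The case on the other side concerns consequence, and much of it stands. Correct keys sit in every row: the cDNA name comes first and the protein name last, and each worked result shows both beside the HG19 string. Appendix VII also defines eligibility by UMD-TP53 classification, and Table 17 describes the classes by functional impact, so the lists are not the only route to the right answer. A laboratory checking the printed reference base against the genome would see the mismatch.

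A reader might infer that sites will enrol subjects with only benign variants, carriers of p.P72R in particular. The documents do not support that. It would require exact chr17-string matching including alleles, an unnoticed mismatch, and a subject whose only TP53 variant is listed; nothing shows that any site works this way. For p.P72R, a worked example gives the correct cDNA and protein names, scores the variant Bg and labels it a common, non-pathogenic polymorphism.

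A reader might also infer that CR, ORR or TP53 VAF results are distorted. The documents give no frequency of subjects with only a listed variant and no count of exposed sites, so this is at most conditional.

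Two limits remain. The Figure 4 graphic is not available here and might name a match key; the criteria printed with it do not. The database's own display convention is also not visible. That could explain how the alleles came to be printed this way, but it would not reconcile them with Table 17, and no readable legend says the chr17 columns use transcript-strand bases.

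**Conclusion.** The chr17 entries are wrong as written under the notation the protocol itself requires: 54 identifiers in 27 rows, plus the HG19 alleles in seven substitution examples and the position order in two indel examples. This is an error of notation; the coordinates themselves are consistent.

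The effect on eligibility is conditional. A laboratory matching exact chr17 strings would find none of the listed variants and could misclassify a subject whose only TP53 variant is listed: a benign missense variant towards eligible, a pathogenic synonymous variant towards not eligible. Other match keys (cDNA, NG, protein, or chr17 position alone) are not affected by the strand error. The number of sites affected is unknown, from 0 to all of up to 10. The 0 of 22 and 0 of 5 results count failed look-ups by that route, not enrolment errors. Severity is low to moderate. It is more than clerical, because these lists operate the defining inclusion criterion.

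The conclusion assumes forward-strand bases in chr17 g. descriptions and no governing match key in the Figure 4 graphic.

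**What to change.** Either of two changes to Appendix VII is enough.

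- **Correct the columns.** Complement the alleles (A↔T, C↔G) in the HG19 and HG38 columns of Tables 18 and 19 and in the HG19 column of the substitution examples, for example chr17:g.7579472G>C for c.215C>G. Put indel ranges in ascending order and complement any inserted base: 7578222_7578223del and 7574004_7574005insT. State that the NM_000546.5 cDNA notation is the governing match key.
- **Delete the columns.** Remove the chr17 columns from the tables and examples, and state that matching is on NM_000546.5 only.

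The cost is a table correction at the next amendment and a notice to site laboratories. No new testing is needed. The notice could ask each laboratory which notation it has matched on, which would replace the 0-to-all range with a count.
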